3.2 Exclusion Criteria

Create a numbered list of the exclusion criteria that define who will be excluded in your study.

- Diagnosis of intellectual disability
- History of known genetic or neurologic disease
- Need for treatment with opioid painkillers
- Weight <25kg
- Inability to swallow pills
- Lack of proficiency in written or spoken English
- Urine drug screen positive for opioids at enrollment
- Positive serum pregnancy test at enrollment
- Lactation
- Elevation of three times the upper limit of normal for age in either alanine aminotransferase (ALT) or asparagine aminotransferase (AST).
- High risk of suicide at enrollment on Columbia Suicide Severity Rating Scale (C-SSRS, for participants age 18)²⁰ or Ask Suicide Screening Questions (ASQ, participants age 13 to 17)²¹
- Current Naltrexone use

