3.3 Early Withdrawal of Subjects

3.3.1 Criteria for removal from study

Insert subject withdrawal criteria (e.g., safety reasons, failure of subject to adhere to protocol requirements, subject consent withdrawal, disease progression, etc.).

- New need for medical hospitalization for malnutrition or eating disorder
- Need for escalation of level of care for eating disorder, that is, requirement for inpatient or residential-level eating disorder care
- New need for opioid painkillers
- Subject consent withdrawal
- Inability to adhere to protocol requirements
- New diagnosis of pregnancy
- New elevation of three times the upper limit of normal for age in either alanine aminotransferase (ALT) or asparagine aminotransferase (AST).

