When patients come into the clinic for either an initial medical screening appointment for their enrollment in PHP or in the initial psychiatry appointment that they have when they enroll, a staff member will assess the patient's eligibility in participating in the research study using the information in the patient's chart and information that is obtained in the appointment. The primary screening criterion will be that the potential subject choses to enroll. Potential subjects who are not medically appropriate for PHP or who do not desire to attend PHP will not be screened any further for the purposes of this study. The only screening that must take place is a point-of-care pregnancy test for postmenarchal (having had at least one menstrual cycle) females with amenorrhea (absent or missed menses)—which is standard of care for these patients regardless of their decision to enroll or not—and a urine drug screen, as oral naltrexone may cause immediate opioid withdrawal if administered to a person with opioid-positive urine. Potential subjects with a positive urine pregnancy test or urine drug screen positive for opioids will not be enrolled. Urine drug screen and urine pregnancy test are specifically outlined in the study consent document.

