5.2 Obtaining Informed Consent

5.2.1 Timing and Location of Consent

Describe where and when the consent process will take place.

Consent and assent will take place at recruitment. Potential subjects will be recruited and enrolled at the completion of either their medical intake appointment for PHP or following the completion of their first psychiatry appointment on their first day of PHP. This will take place in a private therapy or medical room in the Adolescent Medicine and Eating Disorders Clinic, on the 2nd floor of the Briarcrest building.

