5.2.2 Coercion or Undue Influence during Consent

Describe the steps that will be taken to minimize the possibility of coercion or undue influence in the consent process.

Prior to initiating consent for this study, medical procedures, risks and alternative therapy should be discussed with subjects by the medical provider, as is standard of care for partial hospitalization programs for eating disorders. All inclusion and exclusion criteria should be reviewed by the medical provider to verify that the subject meets eligibility criteria prior to enrollment. Consent and assent will take place in a private, neutral environment with the patient and their parent, if the patient is under the age of 18. The study coordinator, not the principal investigator or co-investigator, will enroll the participant in the study and answer all questions. Potential patients under the age of 18 will be asked to provide assent to participate in the study; if they do not wish to provide assent then their parents cannot provide consent on their behalf and therefore "force" the child to participate. Potential subjects who plan to enroll in PHP may do so regardless of their desire to participate in this study, which will be directly told to them in plain, spoken language at time of consent/assent and enrollment, as well as written in the consent form. The decision to participate or not to participate in this study should have no impact on the clinical care the potential subject receives while they complete PHP.

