6.2.1.2 Plan to destroy identifiers or a justification for retaining identifiers

Describe the plan to destroy the identifiers at the earliest opportunity consistent with the conduct of the research. Include when and how identifiers will be destroyed. If identifiers will be retained, provide the legal, health or research justification for retaining the identifiers.

All data will be maintained in RedCAP, and will be accessible only to study members. A key linking study participants to study data will be kept for the duration that the study data are kept, and all research data will be retained per FDA regulation and institutional policy. Data maintained in PennState Health drives will be destroyed in accordance with current data management protocols at our institution and paper records will be securely shredded and incinerated.

6.2.2 Explanation for why the research could not practicably be conducted without access to and use of PHI

Provide an explanation for why the research could not practicably be conducted without access to and use of PHI.

Much of the outcomes to be studied here, including weight restoration, length of time in care, or worsening of depression, are assessed on a regular basis as a part of routine clinical care. Because participants in this study will otherwise be undergoing routine care in PHP, access to PHI would reduce need for duplicate visits for study purposes only and should increase study retention. Additionally, certain inclusion and exclusion criteria, such as lab results, will be available in PHI and help determine participant eligibility.

6.2.3 Explanation for why the research could not practicably be conducted without the waiver or alteration of authorization

Provide an explanation for why the research could not practicably be conducted without the waiver or alternation of authorization.

Because participation in this study requires negative urine drug screen and normal bloodwork prior to enrollment, without being able to evaluate PHI prior to enrollment we will not be able to determine who is eligible without duplicating studies and potentially exposing the patient to excessive risk and pain in the form of duplicate lab studies and blood draws.

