7.1 Study Design

Describe and explain the study design.

This is a double-blind, randomized, placebo-controlled study. We have developed the following schedule of events. All events with a superscript $^{\circ}$ are for study purposes only and are not part of the standard of care:

	Pre-Enrollment Screening: Medical	Enrollment	Week 1	Week 2	Week 3	Week 4	Week 5	Week 6 (end of treatment	Week 8-9 (post- treatment)	Six Months
Intervention								_	>	
Initial Medical Assessment	Х									
Subsequent Medical Assessment, including comprehensive review of systems			x		x		x		х	х
Initial Psychiatry Assessment	X									
Subsequent Psychiatric Assessment, including suicidal ideation			х	х	х	х	х	х	х	х
Discussion of risks and benefits, inclusion and exclusion criteria ^o		х								
Consent/Assent ^o		Х								
\$25 Greenphire Clincardo		Х								х
Urine Drug Screen ^o		Х								
Serum Pregnancy Test (female participants)°		х								
Urine Pregnancy Test (female participants)°					х			х		
Administer Study Article ^o			Х	Х	х	Х	Х	х		
EKG	X									
AST	X				Xº			Xº		
ALT	Х				χ°			Xo		
Total Bilirubin	Х				Xº			Xº		
Direct bilirubin	Х				Xº			Xº		
Heart Rate	Х		Х	Х	Х	Х	Х	Х	Х	Х
BMI	X		Х	Х	Х	Х	Х	X	Х	Х
Height	X		Х	X	X	X	Х	X	X	Х
Weight	X		X	X	X	X	X	X	X	X
Blood Pressure	X		X	X	X	X	X	X	X	X
Temperature Adverse event monitoring ^o	Х		X	x	x	x	x	x	X	X
Suicidal Ideation Screening (ASQ			^	^	^	^	^			
for age <17or C-SSRS for age 18+)		х	Х	Х	х	Х	Х	х	Х	Х
ED-15		Х	х		х			Х	X	х
EDE-Q		Х	х		х			Х	X	Х
ABUSI°		Х	Х		х			Х	Х	Х
GAD-7		Х	х		х			Х	Х	Х
PHQ-9		Х	Х		Х			Х	X	Х
BIS/BAS°		Х	Х		Х			Х	Х	Х

Note: Medical assessments may occur in weeks 1,3 etc or 2,4 etc depending on standard of care for that patient. As long as patients are seen within a 14 day interval (2 week timeframe), the exact week intervals (1,3 or 2,4) may vary. Additionally, the 6 month follow up appointment may take place any time between 5-7 months after study enrollment ends.

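### Section 4.2.4 limits mandatory pregnancy testing to females with amenorrhea, against a serum test in all females elsewhere, and drug release waits for no pregnancy result

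*Combined protocol and SAP*

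**What the plan says.** Section 4.2.4 sets out eligibility screening: "The only screening that must take place is a point-of-care pregnancy test for postmenarchal (having had at least one menstrual cycle) females with amenorrhea". The same sentence adds a urine drug screen, and the next one bars enrollment on a positive urine pregnancy test or an opioid-positive drug screen.

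Other sections describe a different test in a wider group. Section 3.2 lists as an exclusion: "Positive serum pregnancy test at enrollment". The schedule of events in 7.1 has a serum row for female participants in the Enrollment column, marked as study-only, and a urine row at weeks 3 and 6. Section 7.1.1 orders the serum test for female candidates on both enrollment routes (medical and psychiatric appointment). Section 10.0 says it is done in every participant assigned female at birth, and gives possible fetal harm as the reason.

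On timing, section 5.2.1 says: "Potential subjects will be recruited and enrolled at the completion of either their medical intake appointment for PHP", or after the first psychiatry appointment on the first day of the partial hospitalization program (PHP). Sections 7.2 (Study Procedures) and 7.3.3 place randomization at enrollment. Section 5.2.2 adds a general check: "All inclusion and exclusion criteria should be reviewed by the medical provider to verify that the subject meets eligibility criteria prior to enrollment". Section 7.2 then provides study article once the urine drug screen and consent or assent are complete. Section 7.1.2 requires vital signs and a drug screen before the first dose.

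**The concern.** There are two separate problems.

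The first is a contradiction about who must be tested and how. Section 4.2.4 is the section a screener would consult, and it says its list is the only mandatory one. Its amenorrhea condition leaves out females who have not missed a period, whom section 10.0 intends to test.

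The second is that no release step is tied to the pregnancy result. The protocol writes an explicit stop for opioids at dispensing and again before the first dose, but none for pregnancy.

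What is at stake is fetal exposure to naltrexone in a pregnancy that predates enrollment. Section 10.0 notes that a history of sexual activity is more common in the adult program. After enrollment, the next scheduled pregnancy test is the urine test at week 3, by which time dosing has begun.

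**Working it through.** No figure in the plan depends on this point, so the check is a comparison of the texts.

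**Step 1: who is tested, and with what**

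| Section | Who | Test | Stated effect of a positive result |
|---|---|---|---|
| 4.2.4 | postmenarchal females with amenorrhea | point-of-care; urine named as the excluding result | not enrolled |
| 3.2 | no subgroup stated | serum, at enrollment | excluded |
| 7.1 schedule | female participants | serum, at enrollment | none stated |
| 7.1.1, both routes | female candidates | serum | referral for counseling |
| 10.0 | all assigned female at birth | serum, at enrollment | none stated |

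Three sections (7.1, 7.1.1, 10.0) call for the serum test in females. Three more refer to it (3.2, 9.1, 9.4), making six in all. One section (4.2.4) states a narrower mandatory test.

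Section 9.1 supports the wider reading. Three liver-function draws at 4 ml give 3 × 4 = 12 ml. One serum pregnancy test brings this to 12 + 1.5 = 13.5 ml. The cap is 16 ml for males and 18 ml for females. The difference of 18 − 16 = 2 ml covers the 1.5 ml test, with no amenorrhea condition attached.

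**Step 2: can 4.2.4 be read as a pre-consent step only?** No. The same sentence lists the urine drug screen, which the schedule marks as study-only and places at Enrollment. The sentence therefore covers study screening as well as routine clinic care.

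**Step 3: what must be in hand before drug is released**

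| Step | Conditions named | Drug screen named? | Pregnancy result named? |
|---|---|---|---|
| Dispensing (7.2) | drug screen, consent or assent | yes | no |
| First dose (7.1.2) | vital signs, drug screen | yes | no |

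The drug screen is named in 2 of 2, a pregnancy result in 0 of 2.

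**Step 4: does the sequence guarantee a result anyway?** Read together, sections 3.2 and 5.2.2 imply a negative serum result before enrollment. But the serum test is a study-only item in the same Enrollment column as consent, and section 5.2.1 completes consent and enrollment at the end of one appointment, with randomization at enrollment. Nothing says that enrollment, randomization or dispensing waits for the laboratory. Dosing is scheduled from Week 1, so the draw should normally come first, but a draw is not a result.

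**The case against.** The strongest reply is that the intended design is clear: a serum test in all females, with positives excluded. Section 7.1.1 orders the test without any amenorrhea condition, section 3.2 excludes on it, and section 5.2.2 has every criterion verified before enrollment. The dispensing sentence in 7.2 does not claim to be a complete list; it also omits the liver enzymes and suicide risk. Naming the drug screen there has its own reason, since section 4.2.4 says naltrexone can cause immediate withdrawal in someone with opioids in the urine.

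Most of this stands, and it rules out several stronger readings that a reader might infer:

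- *That a known pregnant patient could be enrolled.* Sections 3.2 and 4.2.4 both bar it.
- *That the protocol as a whole leaves females without amenorrhea untested.* Only 4.2.4 does; 7.1.1, if followed, tests them.
- *That 7.1.1 merely refers pregnant candidates, whereas it excludes opioid-positive ones.* The wording differs, but the exclusion is already stated in 3.2 and 4.2.4, so this is style.
- *That the serum test may come a week late on the psychiatric route.* The seven-day window in 7.1.1 governs routine labs. The serum test is a separate study item, mentioned straight after the drug screen, and section 9.4 also has both collected at enrollment.

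Two things are left. The word limiting section 4.2.4 to its own list cannot be reconciled with the other sections. And a general instruction to review criteria does not tell pharmacy or clinic staff to hold the first bottle until a serum result is documented. In the schedule, suicide screening is a questionnaire and the first liver enzymes precede enrollment. The drug screen and the serum pregnancy test are the two study-only laboratory tests in the Enrollment column, and only the drug screen is a named release condition.

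**Conclusion.** The point holds in two limited parts. Section 4.2.4 contradicts the rest of the protocol on which females are tested at enrollment and on which test excludes them. And the two release conditions allow drug to be given out while a serum result is pending, even though a negative result is implied beforehand.

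The practical size is probably small. The documents give no pregnancy rate and no laboratory turnaround time, so no number of exposed participants or doses can be stated. If the serum sample is drawn with the drug screen, the exposure window is the laboratory turnaround only. Other controls limit the consequences: the contraception rule in 7.1.1, the urine tests at weeks 3 and 6, and removal under 3.3.1 for "New diagnosis of pregnancy". The urine tests and removal act only after dosing has started, and the contraception rule does not detect a pregnancy that predates enrollment.

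Efficacy results are not affected. The point should be fixed because it concerns a fetal-safety check and the remedy is cheap.

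**What to change.** 1. In section 4.2.4, state that a serum pregnancy test is obtained at enrollment in all participants assigned female at birth, that the standard-of-care point-of-care test does not replace it, and that anyone with a positive serum or urine test will be neither enrolled nor randomized.
2. In section 7.2 (Study Procedures), add to the dispensing condition a documented negative serum pregnancy result for participants assigned female at birth. Add the same result to the checks before the first dose in section 7.1.2.

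The cost is wording in three places and one check before pharmacy release. No test or blood volume is added: the serum test is already in the schedule and its 1.5 ml is already counted in section 9.1. The downside is that first dispensing may wait briefly for the result.

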5.0 Consent Process and Documentation

Refer to the following materials:

- The "HRP-090- SOP Informed Consent Process for Research" outlines the process for obtaining informed consent.
- The "HRP-091—SOP Written Documentation of Consent" describes how the consent process will be documented.
- The "HRP-314- Worksheet Criteria for Approval" section 7 lists the required elements of consent.
- The "HRP-312- Worksheet Exemption Determination" includes information on requirements for the consent process for exempt research. In addition, the CATS IRB Library contains consent guidance and templates for exempt research.
- The CATS IRB library contains various consent templates for expedited or full review research that are designed to include the required information.
- Add the consent document(s) to your study in CATS IRB (http://irb.psu.edu). Links to Penn State's consent templates are available in the same location where they are uploaded. DO NOT include the actual consent wording in this protocol.

[Do not type here]

5.1	Consent Process:				
	Check all applicable boxes below:				
	☐ Informed consent will be sought and documented with a written consent form [Complete Sections 5.2 and 5.6]				
	Implied or verbal consent will be obtained – subjects will not sign a consent form (waiver of written documentation of consent) [Complete Sections 5.2, 5.3 and 5.6]				
	Informed consent will be sought but some of the elements of informed consent will be omitted or altered (e.g., deception). [Complete section 5.2, 5.4 and 5.6]				
	Informed consent will not be obtained – request to completely waive the informed consent requirement. [Complete Section 5.5]				

5.2 Obtaining Informed Consent

5.2.1 Timing and Location of Consent

Describe where and when the consent process will take place.

Consent and assent will take place at recruitment. Potential subjects will be recruited and enrolled at the completion of either their medical intake appointment for PHP or following the completion of their first psychiatry appointment on their first day of PHP. This will take place in a private therapy or medical room in the Adolescent Medicine and Eating Disorders Clinic, on the 2nd floor of the Briarcrest building.

5.2.2 Coercion or Undue Influence during Consent

Describe the steps that will be taken to minimize the possibility of coercion or undue influence in the consent process.

Prior to initiating consent for this study, medical procedures, risks and alternative therapy should be discussed with subjects by the medical provider, as is standard of care for partial hospitalization programs for eating disorders. All inclusion and exclusion criteria should be reviewed by the medical provider to verify that the subject meets eligibility criteria prior to enrollment. Consent and assent will take place in a private, neutral environment with the patient and their parent, if the patient is under the age of 18. The study coordinator, not the principal investigator or co-investigator, will enroll the participant in the study and answer all questions. Potential patients under the age of 18 will be asked to provide assent to participate in the study; if they do not wish to provide assent then their parents cannot provide consent on their behalf and therefore "force" the child to participate. Potential subjects who plan to enroll in PHP may do so regardless of their desire to participate in this study, which will be directly told to them in plain, spoken language at time of consent/assent and enrollment, as well as written in the consent form. The decision to participate or not to participate in this study should have no impact on the clinical care the potential subject receives while they complete PHP.

5.3 Waiver of Written Documentation of Consent

Review "HRP - 411 - Checklist - Waiver of Written Documentation of Consent."

Indicate which of the following conditions applies to this research: The research presents no more that minimal risk of harm to subjects and involves no procedures for which written consent is normally required outside of the research context. OR The only record linking the subject and the research would be the consent document and the principal risk would be potential harm resulting from a breach of confidentiality. Each subject will be asked whether the subject wants documentation linking the subject with the research, and the subject's wishes will govern. (Note: This condition is not applicable for FDA-regulated research. If this category is chosen, include copies of a consent form and /or parental permission form for participants who want written documentation linking them to the research.) OR

If the subjects or legally authorized representatives are members of a distinct cultural group or community in which signing forms is not the norm, that the research presents no more than minimal risk of harm to subjects and provided there is an appropriate alternative

mechanism for documenting that informed consent was obtained. (Note: This condition is not applicable for FDA-regulated research.) Describe the alternative mechanism for documenting that informed consent was obtained: N/A Indicate what materials, if any, will be used to inform potential subjects about the research 5.3.2 (e.g., a letter accompanying a questionnaire, verbal script, implied consent form, or summary explanation of the research) N/A Informed consent will be sought but some of the elements of informed consent will be omitted or 5.4 altered (e.g., deception). Review "HRP-410-Checklist -Waiver or Alteration of Consent Process" to ensure that you have provided sufficient information. Indicate the elements of informed consent to be omitted or altered 5.4.1 N/A Indicate why the research could not practicably be carried out without the omission or alteration of consent elements N/A 5.4.3 Describe why the research involves no more than minimal risk to subjects. N/A 5.4.4 Describe why the alteration/omission will not adversely affect the rights and welfare of subjects. N/A 5.4.5 If the research involves using identifiable private information or identifiable biospecimens, describe why the research could not be practicably be carried out without using such information or biospecimens in an identifiable format.

N/A

